7 STUDY DEVICE

7.1 Description

The device under investigation is the “Anterior Vertebral Tether Device”, comprised of components from Globus Medical, Incorporated systems: The *Creo® System* and the *Transition™ Stabilization System or SILC™ Fixation System*. From the *Creo® System* come the staples, screws, and locking caps of the investigational device. From the *Transition™ Stabilization System or SILC™ Fixation System* comes the Polyethylene Terephthalate (PET) cord. These four components are part of a 510K-cleared implant system distributed by Globus Medical, Inc. The *Creo®* and *Transition™* Globus systems are classified as Class II under 21 CFR 888.3070, and *SILC™ Fixation System* Globus system is classified as Class II under 21 CFR 888.3010. The devices are manufactured and distributed according to manufacturer guidelines and in compliance with 21 CFR 820.

The entire systems are supplied to CHOP as part of routine surgical treatment. The systems supplied also includes hydroxyapatite-coated titanium alloy Ti6Al4V (ASTM F136) or alloy Ti6Al4Nb (ASTM F1295) pedicle screws, polycarbonate urethane spacers and bumpers, titanium alloy spools, end spools, and set screw ends. The rest of the system will be discarded according to the appropriate CHOP OR policies and procedures.

7.2 Packaging

The device is part of commercially marketed systems from Globus Medical, Inc. As such, the device is packaged according to manufacturer guidelines and in compliance with 21 CFR 820.130.

7.3 Labeling and Tracking

The device is part of a commercially marketed system from Globus Medical, Inc. As such the device will be labeled according to manufacturer guidelines and in compliance with 21 CFR 801.

Specific device label parameters of the staples, screws, locking caps, and PET cord will be tracked by the study team to comply with FDA standards for investigational device tracking. Those parameters include:

- Manufacturer of device
- Model name of device
- Device Part Number
- Device Lot Number

The device will be received and processed in the usual standard process per hospital standard operating procedures. The medical record and device form, which will contain the parameters stated above, will be the source documents for tracking implanted devices. The process for device handling and tracking will be conducted in accordance with our study device tracking SOP.

7.4 Indications for Use

7.4.1 Intent of the Device:

- The device is intended to normalize the vertebral column of those with pediatric idiopathic scoliosis, by applying tensional force.

7.4.2 Patient population:

- Males and females diagnosed with idiopathic scoliosis (all types - infantile, juvenile, adolescent).
- Spina bifida occulta is permitted.
- Spondylolysis or Spondylolisthesis is permitted, as long as it is non-operative, the patient has not had any previous surgery for this, and no surgery is planned in the future.

7.4.3 Curve types:

- We will use the Lenke classification system for curve type. The Lenke Classification system is a classification for AIS. For those subjects with AIS, the Lenke types eligible for inclusion are Lenke types 1, 2, and 3. For those subjects with JIS and IIS (idiopathic scoliosis diagnosed before age 10), subjects with curves patterns that match all other criteria to be classified as Lenke types 1, 2, and 3 will be included.

7.4.4 Levels that will be treated:

- Thoracic levels T4-L1 (i.e., most cephalad and caudad levels that may be treated).

7.4.5 Growth and skeletal maturity assessment:

- Chronological age 8-16 years (inclusive)
- Sanders bone age less than or equal to 4.

7.4.6 Range of curve magnitudes that will be treated:

- Thoracic curve greater than or equal to 35 degrees and less than or equal to 60 degrees
- Lumbar curve less than 35 degrees

8 SAFETY MANAGEMENT

8.1 Clinical Adverse Events

Clinical adverse events (AEs) will be monitored throughout the study.

8.2 Adverse Event Reporting

Unanticipated problems related to the research involving risks to subjects or others that occur during the course of this study (including SAEs) will be reported to the IRB in accordance with CHOP IRB SOP 408: Unanticipated Problems Involving Risks to Subjects. AEs that are not serious but that are notable and could involve risks to subjects will be summarized in narrative or other format and submitted to the IRB at the time of continuing review.

8.3 Definition of an Adverse Event

An adverse event is any untoward medical occurrence in a subject who has received an intervention (drug, biologic, or other intervention). The occurrence does not necessarily have to have a causal relationship with the treatment. An AE can therefore be any unfavorable or unintended sign (including an abnormal laboratory finding, for example), symptom, or disease temporally associated with the use of a medicinal product, whether or not considered related to the medicinal product.

We will use the Clavien-Dindo Classification system [47], as well as the Comprehensive Complication Index (based off of the Clavien-Dindo system) [48] to classify and analyze patient adverse events. **Grade I and Grade II events will be considered AEs. (See Appendix 1 for classification table)**

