SAE	Serious Adverse Event – any undesirable experience associated with use of the medical device that results in

	death, is life-threatening, requires inpatient hospitalization, or prolongs existing hospitalization.
Sagittal spine x-ray	Radiograph of the entire spine taken in the sagittal plane.
Sanders Bone Age	Standardized method of measuring skeletal maturity that is predictive of scoliotic curve progression. This method involves analysis of the ossification centers of the hand, using an AP radiograph of the entire hand.
SOC	Standard of Care
Thoracic/Lumbar flexion test	Subject stands with trunk erect while measuring tape is placed proximally on the spinous process of C7 and distally to S1. The subject then bends forward at the waist, with knees in extension. Following flexion of the vertebrae, using the same bony landmarks, the examiner calculates the difference in distance between the starting and ending positions.
Thoracic/Lumbar lateral flexion test	Subject stands erect with the feet flat on the floor. Place one end of a measuring tape on the tip of the middle finger and the other on the floor on a point directly beneath the middle finger. The patient then laterally flexes their trunk. The difference following the lateral flexion motion is measured.
TLSO	Thoraco-lumbo-sacral Orthosis
UDI	Unique Device Identification
VBT	Vertebral Body Tethering

ABSTRACT

Context:

Scoliosis is a condition in which the spine is deformed by a curvature in the coronal plane. It is generally associated with a twisting (axial plane) deformity as well. It can have a variety of underlying etiologies and the etiology is used to classify the types of scoliosis. Idiopathic scoliosis is sub-classified in two ways: by age of onset and by magnitude of deformity. Curves between 10 and 25 degrees are considered mild. Curves between 25 and 50 degrees are classified as moderate. Curves greater than 50 degrees are termed severe. The current standard of care for moderate scoliosis in patients with remaining growth is to utilize a thoracolumbosacral orthosis (TLSO brace) to prevent progression of deformity. The scientific evidence has supported the efficacy of this intervention in avoiding progression of the Cobb angle to 50 degrees or more.

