8.4 Definition of a Serious Adverse Event (SAE)

An SAE is any adverse event that results in any of the following outcomes:

- death,
- a life-threatening event (at risk of death at the time of the event),
- requires inpatient hospitalization or prolongation of existing hospitalization,
- a persistent or significant disability/incapacity, or
- a congenital anomaly/birth defect in the offspring of a subject.

Important medical events that may not result in death, be life-threatening, or require hospitalization may be considered a serious adverse event when, based upon appropriate medical judgment, they may jeopardize the subject and may require medical or surgical intervention to prevent one of the outcomes listed in this definition.

A distinction should be drawn between serious and severe AEs. A severe AE is a major event of its type. A severe AE does not necessarily need to be considered serious. For example, nausea which persists for several hours may be considered severe nausea, but

would not be considered serious. On the other hand, a stroke that results in only a limited degree of disability may be considered a mild stroke, but would be considered serious.

We will use the Clavien-Dindo Classification system [47], as well as the Comprehensive Complication Index (based off of the Clavien-Dindo system) [48] to classify and analyze patient adverse events. **Grade III (a/b), Grade IV (a/b), and Grade V events will be considered SAEs. (See Appendix 1 for classification table)**

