12 APPENDIX

12.1 Appendix 1: Clavien-Dindo complications classification system (from Dindo, *et al.*)

TABLE 1. Classification of Surgical Complications

Grade	Definition
Grade I	Any deviation from the normal postoperative course without the need for pharmacological treatment or surgical, endoscopic, and radiological interventions Allowed therapeutic regimens are: drugs as antiemetics, antipyretics, analgetics, diuretics, electrolytes, and physiotherapy. This grade also includes wound infections opened at the bedside
Grade II	Requiring pharmacological treatment with drugs other than such allowed for grade I complications Blood transfusions and total parenteral nutrition are also included
Grade III	Requiring surgical, endoscopic or radiological intervention
Grade IIIa	Intervention not under general anesthesia
Grade IIIb	Intervention under general anesthesia
Grade IV	Life-threatening complication (including CNS complications)* requiring IC/ICU management
Grade IVa	Single organ dysfunction (including dialysis)
Grade IVb	Multiorgan dysfunction
Grade V	Death of a patient
Suffix "d"	If the patient suffers from a complication at the time of discharge (see examples in Table 2), the suffix "d" (for "disability") is added to the respective grade of complication. This label indicates the need for a follow-up to fully evaluate the complication.

*Brain hemorrhage, ischemic stroke, subarachnoidal bleeding, but excluding transient ischemic attacks.
CNS, central nervous system; IC, intermediate care; ICU, intensive care unit.

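### Sections 8.3 and 8.4 define an SAE by two rules with no stated precedence, so a Grade I-II event that prolongs the stay or causes readmission can be left out of the SAE count

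*Combined protocol and SAP*

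**What the plan says.** Section 8.4 opens with an outcome test: "An SAE is any adverse event that results in any of the following outcomes". One of the listed outcomes is that the event "requires inpatient hospitalization or prolongation of existing hospitalization". No grade condition is attached.

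Sections 8.3 and 8.4 then close with matched sentences in bold. Under the AE definition: "Grade I and Grade II events will be considered AEs". Under the SAE definition: "Grade III (a/b), Grade IV (a/b), and Grade V events will be considered SAEs".

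Appendix 1 defines the grades by treatment. Grade I is "Any deviation from the normal postoperative course without the need for pharmacological treatment or surgical, endoscopic, and radiological interventions"; Grade II is "Requiring pharmacological treatment with drugs other than such allowed for grade I complications". Length of stay and readmission are not grading criteria.

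The abbreviations list has its own SAE entry, "any undesirable experience associated with use of the medical device that results in" "death, is life-threatening, requires inpatient hospitalization, or prolongs existing hospitalization". It agrees with 8.4 on hospitalization, but it ties the event to use of the device and omits disability and the other 8.4 criteria.

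The SAE label is used in four places:
- Section 6.1: the primary endpoint is the rate of AEs/SAEs.
- Sections 6.6 and 6.6.1: the stopping rule for procedure-related SAEs is 5 of the first 5 patients, 7 of the first 10, or more than 50% after 15 cases.
- Section 8.5: to POD 90 all AEs are recorded; from POD 91 to 730 all SAEs are recorded, but only device-related AEs.
- Section 8.6: timelines for notifying the IRB.

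**The concern.** The outcome rule and the grade rule disagree on one class of event: Grade I or II by treatment, but with a prolonged or repeat hospital stay. The plan expects such events. Section 9.3.2.1 says that a pneumothorax or a bronchopulmonary plug may either lengthen the hospital stay or require intervention. Where only the stay is lengthened, the outcome list makes the event an SAE and the grade sentences make it an AE.

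Safety is the primary objective, the trial has one arm, and at most 40 subjects are planned. Two people applying the protocol in good faith could report different SAE rates from the same charts and carry different tallies into 6.6.1. In the extended follow-up phase the label also decides whether a non-device-related event enters the study record, so a later reclassification from study records could not recover it.

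**Working it through.** **Step 1: the rules side by side.**

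| Event | 8.4 outcome list | 8.3/8.4 grade sentences |
|---|---|---|
| Grade I-II, stay not affected | AE | AE |
| Grade I-II, prolonged stay or readmission | **SAE** | **AE** |
| Grade IIIa, no listed outcome | **AE** (unless judged an important medical event) | **SAE** |
| Grade IV or V | SAE | SAE |

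The rules diverge in both directions. The second row is the one that can lower the SAE count.

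**Step 2: where the label matters.** To POD 90 every AE is recorded (8.5), so a second-row event stays in the overall AE count and only the SAE rate changes. After POD 90, if it is classed as an AE and is not device-related, it is not recorded and leaves both counts.

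**Step 3: effect on the SAE rate.** The plan states no SAE rate, so there is no figure to reproduce and the counts here are assumptions. Exact (Clopper-Pearson) 95% intervals at N = 40:
- 4 patients by grade, 4 more by outcome only: 4/40 = 10% (2.8-23.7%) against 8/40 = 20% (9.1-35.6%).
- 8 by grade, 8 more by outcome only: 8/40 = 20% (9.1-35.6%) against 16/40 = 40% (24.9-56.7%).

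Section 6.3.2 plans exact intervals for device-related AE incidence, not for the SAE rate, so these show scale only.

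**Step 4: effect on the 6.6.1 rule.** Inputs: the thresholds in 6.6.1, N = 40 (Section 6.4), and an assumed per-patient probability p of a procedure-related SAE, independent across patients and known before the next case. Let S(n) be the number of the first n patients with an SAE. Enrollment halts if S(5) = 5, if S(n) is at least 7 at any n up to 10, or if S(n) > n/2 at any n from 15 to 40. Among paths not yet halted, P[S(n)=k] = (1-p)·P[S(n-1)=k] + p·P[S(n-1)=k-1]; the halted mass is summed over n.

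Example of the single thresholds at p = 0.40: 5 of 5 is 0.4^5 = 0.010; at least 7 of 10 is 0.055; at least 8 of 15 is 0.213.

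| p | 5 of 5 | ≥7 of 10 | ≥8 of 15 | Any halt by N = 40 |
|---|---|---|---|---|
| 10% | 0.00001 | 0.00001 | 0.00003 | 0.0001 |
| 20% | 0.0003 | 0.0009 | 0.004 | 0.006 |
| 30% | 0.002 | 0.011 | 0.050 | 0.073 |
| 40% | 0.010 | 0.055 | 0.213 | 0.33 |
| 50% | 0.031 | 0.172 | 0.500 | 0.73 |

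Starting the third check at case 16 lowers the last column only slightly (0.31 at 40%, 0.71 at 50%).

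**Step 5: grade-only count against the combined rule.** Assume that Grade III or higher occurs in 10-30% of patients and that a further 10-30% have only a Grade I-II event with a prolonged or repeat stay.

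| By grade | Combined | Halt, by grade | Halt, combined |
|---|---|---|---|
| 10% | 20% | 0.0001 | 0.006 |
| 10% | 40% | 0.0001 | 0.33 |
| 20% | 30% | 0.006 | 0.073 |
| 20% | 40% | 0.006 | 0.33 |
| 30% | 60% | 0.073 | 0.96 |

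**The case against.** The strongest reply is that the rules add. An SAE is a kind of AE; 8.3 does not call Grade I-II events non-serious or AEs only, and the Grade III-V sentence adds SAEs without removing any. Section 8.4 tells staff to keep serious and severe apart, and 8.5 records seriousness separately from intensity. On that reading a Grade II event that prolongs the stay is both an AE and an SAE, and nothing is lost.

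The reading is possible, but it is not stated, and it leaves the 8.3 sentence with no function: 8.3 already makes every untoward occurrence an AE, and Grades III-V are AEs too. Next to its counterpart in 8.4, the sentence reads as a split. Staff who follow it would be following the text.

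Several limits do stand. A reader might infer that all the stopping rules are affected. The 6.6.2 screw and implant rules require re-operation, as does tether failure to count as an SAE, so a Grade I-II hospital stay does not bear on them. A reader might infer that expedited reporting fails broadly. The text of 8.6 limits prompt notice to unanticipated, related events, and the plan lists pneumothorax and plug as known risks. A reader might also use infection as the example, but Section 9.3.2.1 says nothing about length of stay for infection.

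**Conclusion.** The inconsistency is real and in current text: two rules, no precedence, and a class of expected events on which they disagree. It can lower the reported SAE rate and the 6.6.1 tally, and after POD 90 it can keep a non-device-related readmission out of the study record.

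Its numerical size cannot be taken from the documents. Under the assumed rates, moving from 10% to 20% leaves the chance of a 6.6.1 halt below 1%; the label becomes material to halting when the combined rate reaches about 40%. The tempting stronger conclusion, that these events vanish from the primary endpoint, is not supported. Through POD 90 they remain in the overall AE count, and the primary objective in Section 2.1 concerns the immediate post-operative period. What is at risk there is the SAE part of the result. The loss of whole events is confined to later follow-up and to the grade-based reading.

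**What to change.** Reconcile 8.3 and 8.4 in one statement, placed in 8.4: an event is an SAE if it meets any outcome listed there, whatever its Clavien-Dindo grade, or if it is Grade III-V. Delete the Grade I-II sentence in 8.3, or reword it to say that these events are AEs unless an 8.4 outcome is met. Keep Clavien-Dindo and the Comprehensive Complication Index as severity scales. Align the SAE entry in the abbreviations list with 8.4.

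The change is to protocol wording only; no added visit, test or subject is needed. Any events already classified should be re-read under the single rule. The downside for the sponsor is that the SAE rate may look slightly less favourable.

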8.4 Definition of a Serious Adverse Event (SAE)

An SAE is any adverse event that results in any of the following outcomes:

- death,
- a life-threatening event (at risk of death at the time of the event),
- requires inpatient hospitalization or prolongation of existing hospitalization,
- a persistent or significant disability/incapacity, or
- a congenital anomaly/birth defect in the offspring of a subject.

Important medical events that may not result in death, be life-threatening, or require hospitalization may be considered a serious adverse event when, based upon appropriate medical judgment, they may jeopardize the subject and may require medical or surgical intervention to prevent one of the outcomes listed in this definition.

A distinction should be drawn between serious and severe AEs. A severe AE is a major event of its type. A severe AE does not necessarily need to be considered serious. For example, nausea which persists for several hours may be considered severe nausea, but

would not be considered serious. On the other hand, a stroke that results in only a limited degree of disability may be considered a mild stroke, but would be considered serious.

We will use the Clavien-Dindo Classification system [47], as well as the Comprehensive Complication Index (based off of the Clavien-Dindo system) [48] to classify and analyze patient adverse events. **Grade III (a/b), Grade IV (a/b), and Grade V events will be considered SAEs. (See Appendix 1 for classification table)**

8.4.1 Relationship of AE/SAE to study intervention or device

The relationship of each Event to the study intervention should be characterized using one of the following terms in accordance with CHOP IRB Guidelines: **definitely, probably, possibly, unlikely, or unrelated**. In this case, the “study intervention” is considered to be the surgical intervention and implantation of the medical device (*Anterior vertebral body tethering surgery under general anesthesia with spinal cord monitoring*). This includes (but is not limited to) induction of anesthesia, incision and surgical approach, device implantation, and recovery. **For each SAE, the PI and Safety Officer will make a case-by-case determination on the relationship of the SAE to the study procedure, which will be documented in the study documents.**

There will be further classification of the Event as either “device-related”, “not device-related”, or “uncertain to be device-related”. Device-related adverse events are those events directly related to the integrity, safety, or biomechanics of the implanted device. This can include variables like device breakage or device migration. Other adverse events which are considered not device-related are those that are related to the act of the surgery and medical recovery (anesthesia, incision and surgical approach, post-operative recovery, etc.). This distinction will be indicated in the study documents. **For each Event, the PI and Safety Officer will make a case-by-case determination on whether the Event is “device related”, “not device related”, or “uncertain”. An event which is classified as “device related” will be considered an Adverse Device Effect. Adverse device effects have special reporting guidelines, as outlined below.**

